The study will be a randomized clinical trial comparing the two options for colorectal cancer screening: the commercially available blood test and usual care (reminder to complete FIT). Patients will be randomized (1:1) to receive the offer of a commercially available blood test (intervention) or usual care. Only intervention patients will be consented to the study. Consented patients will be asked to complete a blood draw at the Kaiser Permanente Northwest (KPNW) clinical lab. Our primary analysis will compare rates of colorectal cancer screening (we will consider completion of the blood draw as completion of colorectal cancer screening) in the two study conditions using intention-to-treat data; we will also report the proportion of intervention participants who consent and, among those, the proportion who successfully complete the blood draw.

We will also conduct qualitative interviews with 20-30 intervention patients and/or providers to understand perceived confidence in the blood test and willingness to receive/offer it on an every-three-year basis. Patients will have been offered the blood test option and will have completed the blood test (completers) or have agreed to take part in the study, but did not show to the blood test visit (non-

completers). Providers will be involved in offering colorectal cancer screening to patients and following up on abnormal results, such as primary care providers and GI specialists.

5. Study Population

a. Number of Subjects

We will prospectively identify and recruit 400 patients from KPNW who received, but did not complete, a FIT in the past 3-9 months, and have an upcoming appointment at a KPNW clinic (within 2 – 6 weeks of eligibility determination). Patient identification will be performed on a weekly basis by a CHR analyst. We will overrecruit by up to 10% to account for participant no-shows and screen-failure.

For the qualitative interview component of this study, 20-30 intervention patients and/or providers will be interviewed.

b. Eligibility Criteria

Inclusion Criteria:

- Age 45-75
- Received a FIT test in the last 3-9 months yet did not return their FIT
- Upcoming appointment or willing to reschedule an appointment at KPNW within 2 - 6 weeks
- Able and willing to provide informed consent if in the intervention arm

Exclusion Criteria:

- On do not contact list
- Having a legal authorized representative
- Non-English speakers

c. Vulnerable Populations

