Vulnerable Populations (VPs)	Include/Exclude	Rationale
Pregnant women	Include	Pregnant women aged 45-75 are still eligible for colorectal cancer screening; there are no unique risks to obtaining a blood test among pregnant women.
Children	Exclude	Colorectal cancer screening is not recommended among individuals younger than 45.
Neonates of uncertain viability or nonviable neonates	Exclude	Colorectal cancer screening is not recommended among individuals younger than 45.
Prisoners*	Excluded	The KPNW IRB does not have the appropriate membership to review research involving prisoners.

Other VP	Rationale for Inclusion
Limited English proficiency	We will exclude patients whose language preference is a non-English language.
Decisionally impaired adults	We will exclude patients with a diagnosis of dementia (documented in the electronic health record).

Click or tap here to enter text.

d. Setting

This is not a multi-site study. Study activities will take place at Kaiser Sunnyside Medical Center and KPNW Center for Health Research.

For the qualitative interview component of this study, the interviews with both patients and providers will be conducted via telephone using password encrypted devices and software (e.g. CHR laptop using Microsoft Teams calling functions).

e. Recruitment Methods

The CHR analyst will identify patients eligible for recruitment based on the eligibility criteria outlined above.

1. The eligible population will then be randomized (1:1); randomization will be stratified based on age group (45-49, 50-64, 65+) and colorectal cancer screening history (ever vs. never).
2. Once the patient list has been identified by the analyst, the population will be uploaded into Clinical Conductor for use by research staff to conduct outreach.
3. The research staff will outreach to the patients for recruitment by mail and/or email. The research staff will send an introductory study letter/email and a copy of the consent form to participants allocated to the intervention condition. Research staff will then call the patient for recruitment.
 - a. A maximum of three calls will be made
4. Research staff will coordinate meeting the patient prior to or after their clinical visit.
5. Outcomes of patient contacts will be tracked (declined, not able to reach, etc.) outcomes into Clinical Conductor.
6. The project analyst will pull data when the project is complete.
 - a. From clinical conductor
 - b. From Virtual Data Warehouse (VDW) datasets

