For the qualitative interview component of this study, for patient completers of the blood test, we will identify a list of recent completers and reach out via letter and/or email. These

possible interviewees will have been informed of the possible interview at their initial consenting process when participating in the blood test.

For non-completer patients, we will generate a list of those who agreed to participate but did not show for their blood collection visit and reach out via letter and/or email.

In both cases, qualitative staff will follow up with up to 3 phone call attempts to ascertain willingness for the interview or not. The recruitment letter/email provides individuals with study team contact information through which they can opt-out of further contact or outright decline.

For provider interviews, we will work with the CHR study PI and study analysts to generate a list of primary care and GI providers who are involved in offering CRC screening and follow up surveillance. Providers will be sent an email request and study staff will follow up by email or phone up to 3 times to ascertain interest in the interview.

f. Consent

Written consent will be obtained prior to any study procedures, for patients in the intervention arm.

An IRB waiver of informed consent will be obtained for patients in the usual care group. Usual care patients will not be asked to sign informed consent, as it may create unnecessary confusion. Outcome data will be collected through retrospective chart review for participants in both study conditions.

For the qualitative interview component of this study, we request a waiver of *signed* informed consent. Verbal consent will be obtained from the patients and providers for participation in the qualitative interviews.

Informed Consent Process

Patients will be mailed and/or emailed copies of the consent forms prior to the research visit so that they can be thoroughly reviewed and discussed with family and friends, if they choose. Patients are also given contact information so that they can contact research personnel by telephone throughout the study. Patients will be interviewed and consented in private. All discussions with patients will be held in strictest confidence and out of earshot of the general public.

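### Willingness to consent is an eligibility rule for one arm only, learned after randomisation, and the waivers leave out intervention patients who do not consent; both conflict with the intention-to-treat analysis

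*Protocol*

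**What the plan says.** **Order of events (Protocol 5e, Recruitment Methods).** An analyst selects patients from records using the eligibility criteria. Step 1 then reads "The eligible population will then be randomized (1:1". Only at step 3 does the intervention arm receive a letter, a consent form and up to three calls. Step 5 expects some of these approaches to fail: "Outcomes of patient contacts will be tracked (declined, not able to reach, etc".

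**Eligibility (5b).** The inclusion list nevertheless contains "Able and willing to provide informed consent if in the intervention arm".

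**Permissions (5f, 5g).** For the intervention arm, "Written consent will be obtained prior to any study procedures, for patients in the intervention arm", and a signed HIPAA authorization is expected from every patient allocated to the blood test. For usual care, "An IRB waiver of informed consent will be obtained for patients in the usual care group", and the HIPAA waiver request likewise names that group only.

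**Analysis (4, 7a).** The primary endpoint is screening by blood test, stool test or colonoscopy within 3 months of randomisation, compared by intention to treat. Section 4 describes what is randomised as an offer: "Patients will be randomized (1:1) to receive the offer of a commercially available blood test (intervention) or usual care". It adds that "we will also report the proportion of intervention participants who consent". On data sources, 5f says "Outcome data will be collected through retrospective chart review for participants in both study conditions".

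**The concern.** An inclusion criterion should be assessable before allocation and apply equally to both arms. This one does neither: it refers to an arm not yet assigned and to a willingness not yet asked about. Read literally, an intervention patient who refuses was never eligible, while the same kind of patient in usual care stays in the denominator. People who refuse a screening offer may well be less likely to be screened by any route, so removing them from one arm would flatter the blood test.

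The permissions create a second route to the same asymmetry. A patient who declines or cannot be reached will not sign an authorization, and the waivers do not extend to that patient. Yet intention to treat needs to know whether that patient returned a stool test or had a colonoscopy. If those charts cannot be read, the patient is either lost or counted as unscreened. Losing the patient tends to favour the blood test; counting the patient as unscreened works against it.

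**Working it through.** **1. The plan's own figure.** Section 7a gives 91.8% power with 200 per group, 88% adherence and an 8-point difference. Exact enumeration of the pooled z test for 88% against 96% gives 91.8% with a one-sided 5% test and 85.4% with a two-sided one. The protocol states neither alpha nor sidedness. This calculation assumes 200 against 200 analysed, and keeping all randomised patients leaves it unchanged.

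**2. The passages side by side.**

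| Question for an intervention patient who declines or is not reached | Pointing to retention | Pointing the other way |
|---|---|---|
| In the trial? | Offer is randomised; consent proportion reported (4); acceptance is an exploratory endpoint (7a) | Fails an inclusion criterion (5b) |
| Chart may be read? | Chart review in both conditions (5f) | Waivers name usual care only (5f, 5g); authorization expected from every allocated patient (5g) |
| In the denominator? | Intention to treat (4, 7a) | 10% over-recruitment allowed for no-shows and screen failure (5a); a sample planned from each of 200 patients, the size of the whole arm (7) |

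No section says that such patients are dropped, and none states the permission under which their outcomes are collected.

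**3. Effect on the test if they were dropped, with no true effect.** From the protocol: 200 per arm, up to 10% more (220), and the 88% rate. Assumed: 20 intervention patients removed; overall rates *r* of 20% and 50% as alternatives to 88%; removed patients screened at *f* times the overall rate; two-sided 5% pooled z test, evaluated by exact binomial enumeration.

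Kept-arm rate = (220*r* − 20*fr*)/200. For *f* = 0.5 and *r* = 0.88: (193.6 − 8.8)/200 = 0.924, an apparent difference of 4.4 points.

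| *f* | *r* | Kept-arm rate | Apparent difference | Rejects, 200 vs 200 | Rejects, 200 vs 220 |
|---|---|---|---|---|---|
| 0.5 | 20% | 21.0% | 1.0 point | 5.8% | 5.7% |
| 0.5 | 50% | 52.5% | 2.5 points | 8.0% | 8.1% |
| 0.5 | 88% | 92.4% | 4.4 points | 31.1% | 32.1% |
| 0 (ceiling) | 20% | 22.0% | 2.0 points | 7.9% | 7.8% |
| 0 (ceiling) | 50% | 55.0% | 5.0 points | 17.2% | 17.7% |
| 0 (ceiling) | 88% | 96.8% | 8.8 points | 93.1% | 94.3% |

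With *f* = 0.75, rejection at 200 vs 200 is 5.3%, 5.8% and 10.6%. With all kept (220 vs 220) it is 5.0%, 5.1% and 5.0%. The 93% ceiling is unlikely: at 88%, only 220 × 0.12 = 26.4 non-completers are expected, and all 20 removed patients would have to be among them.

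**4. Effect on the estimate when the blood test works.** The protocol gives no consent rate. Assume 50% consent, 90% of consenters complete the draw, and both usual care and non-consenters are screened at 15%.

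- Intention to treat: 0.5 × 0.90 + 0.5 × 0.15 = 0.525; difference 0.525 − 0.15 = 37.5 points.
- Non-consenters dropped: 0.90 − 0.15 = 75 points.
- Non-consenters kept but counted as unscreened: 0.45 − 0.15 = 30 points.

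**The case against.** The strongest reply is that the analysis set is already settled. The offer is what is randomised, intention to treat is stated twice, the proportion consenting is reported, and chart review covers both conditions. The protocol also uses the word participants for allocated patients who have not yet consented, so the chart-review sentence can be read to include decliners. On this view the consent bullet only marks who must sign, and no procedure removes anyone by it. The waiver gap is then a regulatory drafting matter that does not define an analysis set, and the IRB's determinations are not shown.

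Much of this stands. Retention is probably what was intended, and nothing here shows that permission is lacking. It is also fair that the large rejection figures depend on the 88% rate, which sits oddly with a population selected for not returning a FIT; at 20% the inflation is small. The figure of 20 removed borrows the over-recruitment allowance, which is not a refusal rate.

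It does not remove the conflict. A patient who fails an inclusion criterion can be classed as a screen failure without anyone feeling that intention to treat was breached, and the protocol over-recruits for screen failure. The rule of a signed authorization from every allocated patient cannot be met for those who decline. An analysis plan can define denominators, but it cannot widen a waiver.

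**Conclusion.** The concern holds as an internal conflict that should be fixed. The eligibility criterion and the authorization rule, if followed as written, would remove patients or outcomes from the intervention arm only, while the analysis text requires them. The protocol does not state that exclusion, and if all randomised patients are analysed as allocated there is no such bias.

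The size is conditional on the stated assumptions. With modest removal and no true effect, false rejection ranges from barely above nominal at a 20% screening rate to roughly 31% at the protocol's own 88%. If the blood test works and many decline, distortion of the estimated difference matters more and can go in either direction. Confidence in the conflict itself is high; it rests on the text and not on these figures.

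**What to change.** - **Eligibility (5b):** remove the arm-specific consent criterion and make consent a condition of the blood draw only.
- **Analysis set (4, 7a):** state that all randomised patients in both arms form the primary denominator as allocated. Decliners, unreached patients and no-shows are counted by their chart outcome and are not replaced.
- **Permissions (5f, 5g):** ask the IRB to extend the consent and HIPAA waivers for chart review to intervention patients who do not consent, and limit the signed-authorization sentence to those who do. State how their outcomes will be handled if the IRB does not agree.
- **Secondary wording:** define the 400 (up to 440) as patients randomised, all analysed; over-recruitment is then compatible with intention to treat. In section 7, plan up to 200 blood samples, matching the funder's cap on tests. With 220 in the arm, 200 samples would need 200/220 = 91% of those allocated to both consent and complete the draw.

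The cost is protocol wording plus an IRB amendment. The intervention-arm completion rate will be lower than among consenters alone, and there will probably be fewer than 200 samples.

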Protocol Title: Study of Colorectal Cancer Screening Options

Study Protocol: 5/09/2019

PI: [name]

NCT05987709

1. Protocol

Title: Study of Colorectal Cancer Screening Options

PI: [name]

2. Objectives

We propose to evaluate Guardant Health's commercially available colorectal cancer screening assay (Guardant SHIELD) in individuals who are not up to date with CRC screening.

Primary Objective (or Aim)

Assess colorectal cancer screening completion among patients who are non-adherent after receiving stool test outreach, who have an upcoming clinical appointment, and who are offered a commercially available colorectal cancer blood test versus usual care (i.e. reminder to complete stool testing during their clinical appointment).

Secondary Objectives (or Aim)

Assess patients' and providers' perceived confidence in the test (based on available test performance characteristics) and willingness to obtain/offer the test on an on-going basis, based on qualitative interviews; assess preliminary rates of follow-up colonoscopy completion (after an initial abnormal test result) among participants allocated to the blood test vs. usual care condition.

3. Background Information and Rationale

Blood-based tests for colorectal cancer detection are thought to offer many advantages over stool-based and endoscopy-based tests. Such tests can be easily completed during in-person clinic visits and can be combined with other blood draws. Such tests may be particularly acceptable for patients who forgo stool-based testing options due to the 'yuk' factor. While blood-based tests will likely produce greater colorectal cancer screening adherence than stool-based testing and endoscopy options, there is little empirical data to support this claim.

4. Study Design

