Qualitative interviews will be conducted among a subset of patients who have (completers) and have not completed (non-completers) the blood test and among providers (20-30 total interviews) who offer colorectal cancer screening to patients. Each participant will undergo a single interview, conducted via telephone, that will last for 45-60 minutes. Each interview will be audio recorded with participant consent.

a. Data Analysis

Data analysis will be conducted at KP CHR will guidance from the statistician at Guardant Health.

Below is a list of primary and secondary endpoints for analyses.

1. Primary endpoint:
 - a. Colorectal cancer screening completion (incl. blood test, stool-test or colonoscopy) rate within 3 months of randomization, by study condition (using intention-to-treat design).
2. Exploratory endpoint:
 - a. Percent of individuals offered blood-based testing who accepted, percent who complete the test.
 - b. Test positivity rate, % of positive individuals who proceeded to diagnostic endoscopy

For those with endoscopy, percent with findings (colorectal cancer, adenoma, negative). Exploratory endpoints will not be statistically powered for comparisons.

Sample size calculation:

Sample size was calculated based on a previous study (Liles, et al 2016). Assuming that the adherence rate of FIT is 88%, a sample size of 200 in each group (FIT and blood test) achieves 91.8% power to detect an adherence rate difference of at least 8% between the two groups.

b. Qualitative Analysis

All interview recordings will be transcribed verbatim. All transcribed interviews will be coded using thematic data analysis and the constant comparative method to identify patterns in interviewees' responses. Code books will be developed for the patient and clinical staff interviews based on an initial review of the transcripts, and the interview guide questions. Codes will be applied to transcripts with the aid of a qualitative software program (e.g., ATLAS.ti) or using a template built in excel. Coding will be an iterative process with the goal of identifying connections and patterns across participants' responses. Emergent themes from the interviews will help us understand both patient and provider acceptability of the blood test as a CRC screening method, and aid in identification of barriers and facilitators to implementing the blood test option within a health system.

c. Sharing of Results with Subjects

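### The sample size assumes 88% FIT adherence in a trial that enrols only people who left a FIT unreturned, so the stated 91.8% power is unsupported for this population

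*Protocol*

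**What the plan says.** The sample size paragraph in Protocol section 7a (Data Analysis) rests on one earlier study: "Assuming that the adherence rate of FIT is 88%, a sample size of 200 in each group (FIT and blood test"), which it says "achieves 91.8% power to detect an adherence rate difference of at least 8% between the two groups". It gives no alpha or sidedness, and does not describe the earlier study's population, setting or outcome window.

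The design that this calculation serves is set out elsewhere in the Protocol:

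- **Population.** The second inclusion criterion in section 5b is "Received a FIT test in the last 3-9 months yet did not return their FIT". Section 5a repeats it: "We will prospectively identify and recruit 400 patients from KPNW who received, but did not complete, a FIT in the past 3-9 months".
- **Control condition.** The primary objective in section 2 compares the blood-test offer with "usual care (i.e. reminder to complete stool testing during their clinical appointment").
- **Endpoint.** Section 7a: "Colorectal cancer screening completion (incl. blood test, stool-test or colonoscopy) rate within 3 months of randomization", by intention to treat.
- **Order of events.** In section 5e, "The eligible population will then be randomized (1:1"); mailing, telephone calls and consent come afterwards. Intervention patients who decline or cannot be reached therefore stay in the denominator.

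**The concern.** Every person in the trial qualifies by not having returned a FIT. Planning the control arm at 88% FIT adherence assumes that nearly nine in ten of them will do so after a reminder. The Protocol gives no reason to expect this. The planning quantity also differs from the endpoint: one is FIT adherence, the other is completion of any screening test within 3 months of randomisation.

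The intervention side is equally demanding. Eight points above 88% is 96%, so about 8 expected non-completers among 200 people randomised before anyone contacted them. The Protocol itself makes provision for patients who decline, cannot be reached or miss the blood draw.

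This matters because the variance of a proportion depends on its level. A rate of 88% lies near the edge of the scale, where variance is small and 8 points are comparatively easy to detect. If usual-care completion lies well inside the scale, 200 per arm gives much less power for 8 points. A non-significant result could then be taken, on the strength of the 91.8%, as good evidence against an 8-point gain when it is not.

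**Working it through.** **Inputs from the Protocol.** n = 200 per arm, 1:1 allocation, control rate 0.88, difference 0.08, stated power 0.918 (sections 4, 5a and 7a). Alpha and sidedness are not given beside the figure, so 5% was tried both ways. The direction is not given either; blood test higher means 0.96.

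**Method.** Two-proportion z-test with pooled variance under the null. Power is by exact binomial enumeration (summing the probability of every pair of counts that rejects), with the normal approximation as a check:

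power ≈ Φ[(d − z·s0)/s1], where s0 = √(2·p̄(1−p̄)/n), s1 = √(p1(1−p1)/n + p2(1−p2)/n), d = p2 − p1 and p̄ = (p1+p2)/2.

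**Step 1: reproduce 91.8%.** For 0.88 vs 0.96, p̄ = 0.92.

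- s0 = √(2 × 0.92 × 0.08 / 200) = 0.02713
- s1 = √(0.88 × 0.12/200 + 0.96 × 0.04/200) = 0.02683
- One-sided 5%: (0.08 − 1.645 × 0.02713)/0.02683 = 1.318, so power 0.906. Exact: 0.9184, which matches the stated figure.
- Two-sided 5%: (0.08 − 1.960 × 0.02713)/0.02683 = 1.000, so power 0.841. Exact: 0.854. Other two-sided 5% methods run from about 79% (continuity-corrected) to 87% (likelihood ratio); none reaches 91.8%.
- With the blood test lower (0.80), the normal approximation gives 0.706 one-sided and 0.588 two-sided.

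So the arithmetic is sound for 88% vs 96% at one-sided 5%. A two-sided 10% test uses the same critical value and gives the same power.

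**Step 2: change only the base rate.** The Protocol gives no usual-care rate for FIT non-returners, so the rates below are assumptions. Exact power for a gain of 8 points, 200 per arm:

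| Usual care | Blood test | One-sided 5% | Two-sided 5% |
|---|---|---|---|
| 4% | 12% | 91.8% | 85.4% |
| 5% | 13% | 88.7% | 81.0% |
| 10% | 18% | 75.4% | 64.3% |
| 20% | 28% | 59.3% | 46.7% |
| 30% | 38% | 52.1% | 39.6% |
| 50% | 58% | 48.1% | 36.3% |
| 87% | 95% | 88.7% | 81.0% |
| 88% | 96% | 91.8% | 85.4% |

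The normal approximation agrees within 0.013 at 5 to 50%. As a worked line at 10%, two-sided: p̄ = 0.14, s0 = 0.03470, s1 = 0.03447, (0.08 − 1.960 × 0.03470)/0.03447 = 0.348, power 0.636.

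4% vs 12% is the mirror image of 88% vs 96%, hence the same power. On the one-sided basis, the stated power for 8 points is reached only at a usual-care rate of about 4% or lower, or 88% or higher.

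**Step 3: what 200 per arm can detect.** Difference detectable with 80% power (normal approximation):

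| Usual care | Two-sided 5% | One-sided 5% |
|---|---|---|
| 10% | 10.0 points | 8.7 points |
| 20% | 12.3 points | 10.8 points |
| 30% | 13.5 points | 11.9 points |

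Larger gains are well covered: 10% vs 22% has about 91% power two-sided.

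**The case against.** **A source is cited, and it cannot be examined here.** That is so, and nothing here says the earlier study's 88% was wrong for its own population. What stands is narrower: the Protocol does not explain why the rate would transfer to people selected for not returning a FIT, or to an any-modality endpoint.

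**The shortfall depends on assumed rates and on holding the gain at 8 points.** This is also fair. At a 3% usual-care rate, power for 8 points is about 95% one-sided and 90% two-sided. The Protocol speaks of a difference of at least 8%, and a gain of 15 points would have about 86% power or more (two-sided 5%) at usual-care rates of 10 to 50%. This rules out calling the trial underpowered. It does not supply a basis for the printed 91.8%: if usual-care completion proves very low, the stated power would hold by luck and not by planning.

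**Alpha and sidedness may be in a statistical analysis plan that is not at hand.** Agreed. Their absence is not counted as a defect; they matter here only because the 91.8% cannot be interpreted without them.

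**Misreading a null result presumes a reader who ignores the confidence interval.** In part. The interval would show the true precision, but a stated design power is often relied on in discussion.

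**Over-recruitment of up to 10% is left out.** It changes little: with 220 per arm and 10% usual care, two-sided power for 8 points rises from about 64% to 68%.

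**Conclusion.** The concern holds. The 91.8% is correct arithmetic for 88% vs 96% at one-sided 5%, but neither 88% nor 96% is justified for a population made up entirely of FIT non-returners, followed for 3 months for any screening test by intention to treat. Over assumed usual-care rates of 5 to 50%, power for 8 points is 89% down to 48% one-sided, or 81% down to 36% two-sided. These rates are illustrations, since the Protocol gives none.

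This does not show that 400 patients are too few; a gain well above 8 points would be detected. It does show that the stated power should not be relied on, in planning or in reading a null result. It should be fixed, and that can be done without changing the design.

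**What to change.** Keep 400 patients and rewrite the sample size paragraph in section 7a:

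1. Replace 88% with an estimate of 3-month completion by any modality under usual care, among health-system patients whose FIT has been unreturned for 3 to 9 months. Section 5e already lists data "From Virtual Data Warehouse (VDW) datasets" for the final analysis; the same source should be able to give this rate, though the Protocol does not say that such a query has been made.
2. State alpha and sidedness next to the power figure.
3. Give the intention-to-treat difference that 200 per arm can detect over a plausible range of that rate, for example 10.0, 12.3 and 13.5 points at 10, 20 and 30% (80% power, two-sided 5%).
4. Keep the 88% and 91.8% only as a record of how the number was chosen, with the one-sided 5% basis (or the equivalent two-sided 10%) if the sponsor confirms it.

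The cost is a records query and one reworded paragraph, with no extra patients and no change to endpoint or procedures. The price is a less favourable stated power for 8 points unless the usual-care rate proves to be about 4% or lower, or 88% or higher, and lower again if a two-sided 5% test is chosen.

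### Does the printed 91.8% power need correcting because the protocol names no significance level, sidedness or test beside it?

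*Protocol*

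**What the plan says.** The sample size paragraph in section 7a of the protocol starts from a previous study: "Assuming that the adherence rate of FIT is 88" per cent. It then takes "a sample size of 200 in each group (FIT and blood test") and states that this "achieves 91.8% power to detect an adherence rate difference of at least 8% between the two groups". No alpha, sidedness or test is given there or elsewhere in the protocol.

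The primary endpoint in the same section is a screening completion "rate within 3 months of randomization, by study condition (using intention-to-treat design"). Section 4 (Study Design) says "Our primary analysis will compare rates of colorectal cancer screening" in the two conditions. Neither sentence gives a direction for the test. Section 3 (Background Information and Rationale) expects a gain: blood-based tests "will likely produce greater colorectal cancer screening adherence than stool-based testing and endoscopy options, there is little empirical data" to support that expectation. Section 5a adds a recruitment margin: "We will overrecruit by up to 10% to account for participant no-shows and screen-failure".

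**The concern.** A power figure has meaning only for a given level and test. Many readers would assume two-sided 5%, and at that level 88% versus 96% with 200 per arm does not give 91.8%. If the trial is in fact analysed that way, the chance of missing the planned gain is about 14-16% with uncorrected Z tests and 19-21% with Fisher's test or a continuity correction. The printed figure implies about 8%.

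The level can also decide how a borderline result is read. With 176/200 screened in usual care and 187/200 in the blood-test arm, the two-sided p-value lies between 0.055 and 0.084 for every common test. That result passes one-sided 5% and fails two-sided 5%. The wording adds to the doubt: the power sentence speaks of a difference without direction, while 91.8% fits only a rise. For 88% versus 80%, pooled Z power is 71.0% at one-sided 5% and 59.6% at two-sided 5%.

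**Working it through.** **Inputs.** Control rate 0.88, difference 0.08 and 200 per group, all from the sample size paragraph in section 7a. Allocation is 1:1 (section 4). The alternative is taken as 0.96, because section 3 expects a gain. The level is not given, so both one-sided 5% (critical value 1.645) and two-sided 5% (1.960) are tried.

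**Normal approximation, pooled Z.** Power = Φ[(d − c·SE0)/SE1], where c is the critical value.

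- Mean rate = (0.88 + 0.96)/2 = 0.92
- SE0 = √(2 × 0.92 × 0.08/200) = 0.02713
- SE1 = √((0.88 × 0.12 + 0.96 × 0.04)/200) = 0.02683
- One-sided 5%: (0.08 − 1.645 × 0.02713)/0.02683 = 1.318, power 90.6%
- Two-sided 5%: (0.08 − 1.960 × 0.02713)/0.02683 = 1.000, power 84.1%

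The unpooled version, Φ(d/SE1 − c), gives 90.9% and 84.6%.

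**Exact power.** This sums the probabilities of all pairs from Binomial(200, 0.88) and Binomial(200, 0.96) for which the test rejects.

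| Test | One-sided 5% | Two-sided 5% |
|---|---|---|
| Pooled Z | 91.8% | 85.4% |
| Unpooled Z | 91.8% | 86.1% |
| Mid-p | 91.8% | 85.4% |
| Likelihood ratio | 92.2% | 86.6% |
| Arcsine | 92.2% | 86.8% |
| Fisher, continuity-corrected Z | 88.9% | 81.3% |

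The printed figure is therefore reproduced to the decimal by the exact Z test at one-sided 5%. With inputs of exactly 88% and 96%, no two-sided 5% test in the table exceeds 86.8%.

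**Is the implied level certain?** The protocol prints 88% and 8% without decimals. As an assumption, suppose the unrounded inputs were 88.4% and a gain of 8.4 points (0.884 versus 0.968). Exact two-sided 5% power with 200 per arm is then 91.3% (pooled Z), 91.8% (unpooled Z) and 92.4% (arcsine). With 88.49% and 8.3 points, the arcsine test gives 91.9%. These readings need both inputs to have been rounded down, so one-sided 5% is the simpler explanation. They show, however, that the level is inferred and not established.

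**Effect of over-recruitment.** If the full 10% were randomised and retained (220 per arm), exact power for 0.88 versus 0.96 at two-sided 5% would be 88.8% (pooled Z), 89.2% (unpooled Z) and 85.5% (Fisher).

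**The borderline example.** Pooled rate = 363/400 = 0.9075 and difference = 11/200 = 0.055. So z = 0.055/√(2 × 0.9075 × 0.0925/200) = 0.055/0.02897 = 1.898, and two-sided p = 0.058. Under 88% versus 96%, the probability that a result falls between the two levels is 5.3% to 7.6%, depending on the test.

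**The case for a change.** The strongest case for acting is that the protocol does more than stay silent. It prints a power to one decimal, and that precision ties the figure to a particular level and direction which the reader cannot see. The funder makes the assay and its statistician guides the analysis (section 7a), so a level written down beforehand would protect the trial from any suggestion that it was chosen after the data were seen. The repair would be one sentence.

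Part of this stands. The protocol on its own does not tell a reader what 91.8% means, and stating the level beside it would be good practice. The rest does not carry a finding:

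- No stated alpha is contradicted, and 91.8% is right at one-sided 5%. If the analysis plan sets that level, nothing is overstated; the harm arises only if two-sided 5% is used, and no section says so.
- The argument from direction asks too much of ordinary wording. Power is normally quoted at one alternative even for a two-sided test, and the background makes clear that the alternative is a gain. The 88% versus 80% figures answer a question the protocol did not ask.
- The documents do not favour two-sided 5% over one-sided 5%, so replacing the figure with about 85% would be a reviewer's choice and not a correction.
- The borderline example was picked to fall in a narrow band, which has a probability of 5.3% to 7.6% under the planning assumption.

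**Conclusion.** The concern does not call for a change. The 91.8% is not an arithmetic error: it equals the exact Z-test power for 88% versus 96% with 200 per arm at one-sided 5%, and rounded inputs could also produce it at two-sided 5%. What is absent is the level, sidedness and test, which a protocol may leave to the statistical analysis plan and which analysts settle there as a matter of course.

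If that plan uses two-sided 5%, and the inputs are exactly 88% and 96%, the printed power is high by 5.7 to 6.4 points with the exact Z tests (91.8 − 86.1 and 91.8 − 85.4) and by 10.5 points with Fisher's test (91.8 − 81.3). Power would still be about 84% or more with uncorrected tests, and the sample size, recruitment and endpoint would stay as they are. This conclusion takes the 88% control rate as given. Whether that rate is plausible for patients who did not return a FIT was not examined here, and it would affect the true power at either level.
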